4.4.1.1.9. Continuous Glucose Monitoring Curves

The MBD and mistimed bolus dose will be calculated using CGM plots and algorithm explained in Section 4.3.1.1. The association between MBD and mistimed bolus doses with time in range (TIR), time above range (TAR), time below range (TBR), and HbA1c will be analyzed using Spearman rank order correlation.

4.4.1.1.10. Participant and Healthcare Professional Questionnaires

Each question from participant and HCP questionnaires will be summarized in a table using frequency and percentages. Participant questionnaire summaries at Visits 1 (baseline) and Visit 3 (end of Study Period 1) from Study Period 1 will be compared to summaries at Visit 7 from Study Period 2 using shift tables. HCP questionnaire summaries will compare initial to end of study. No formal statistical testing is planned.

4.5. Exploratory Endpoints Analysis

4.5.1. Summary Statistics of Actual and Change in HbA1c

Actual HbA1c values at baseline (Visit 1) and Visit 7 and change from baseline will be presented in a table using descriptive continuous statistics. In addition, an MMRM will be run on this data. Example SAS Software version 9.4 program code for the MMRM is as follows:

```
proc mixed data = <data>;
    Class StudyPeriod usubjid week;
    Model HbAlc_change = StudyPeriod BaseBMI BaseHbAlc week/ ddfm = kenwordroger;
    Random usubjid / subject = usubjid;
    Repeated week/ subject = usubjid type = un rcorr;
    Lsmeans StudyPeriod/diff cl pdiff;
run;
```

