## 1.3. Schedule of Activities

Table 1.1 summarises the Schedule of Activities (SoA) for the study.

Table 1.1. Schedule of Activities for Study F3Z-MC-IORW

	Study Pe	eriod 1 (Masl	ked)	Stu	Study Period 2 (Unmasked)				UNS	ET
Visit Number	V1	V2	V3	V4	V5	V6	V7	V8 or ET(Exit)		
Visit Type	On-site	Remote	On-site	Remote	Remote	Remote	On-site	Remote		
Time from previous visit (weeks or days)	N/A	1 W	5 W	1 W	3 W	4 W	4 W	3D	N/A	N/A
Visit window (days)	N/A	+/-3	+7	+/-3	+/-3	+/-3	+7	+/-1	N/A	N/A
Study Logistics	-	 		<del>-</del>	-				-	
Informed Consent signed	X									
Eligibility Criteria Reviewed	X									
Enrolment	X									
Install and set-up Glooko RMA	X									
Pair the Tempo Smart Button	X									
Study CGM device user training provided	X									
Study phone user training provided	X									
Complete Participant Training	X									
Participant brings mobile device with RMA and Tempo Pen with Tempo Smart Button			X				X			X
Confirm Tempo Smart Button transfer onto Glooko RMA			$X^1$		$X^1$	X 	$X^1$		X 	X 
Review the functioning, understanding, and use of the study platform components	X	X	X	X	$X^2$	$X^2$			$X^2$	

	Study Per	Period 1 (Masked)			ıdy Period	2 (Unmask	ed)	Follow-up	UNS	ET
Visit Number	V1	V2	V3	V4	V5	V6	V7	V8 or ET(Exit)		
Visit Type	On-site	Remote	On-site	Remote	Remote	Remote	On-site	Remote		
Time from previous visit (weeks or days)	N/A	1 W	5 W	1 W	3 W	4 W	4 W	3D	N/A	N/A
Visit window (days)	N/A	+/-3	+7	+/-3	+/-3	+/-3	+7	+/-1	N/A	N/A
Unmask Tempo Pen data in Glooko RMA			X							
Clinical Assessment and Diab	etes Management									
Medical History (including pre-existing conditions)	X									
Demographic information	X									
Height and Weight	X		$X^3$				$X^3$			$X^3$
Physical Examination	X									
Urine PoC Pregnancy Test (WOCBP only)	X									
HbA1c PoC Test	X						X			X
Vital Signs	X									
Hypoglycaemia management and training	X		$X^4$		$X^4$	$X^4$			X 	QR
Review concomitant medications	X	X	X	X	X	X	X	X	X	X
Review Adverse Events	X	X	X	X	X	X	X	X	X	X
Review Device Deficiencies (DD)	X	X	X	X	X	X	X	X	X	X
Review of glucose values and insulin regimen with participant (adjust if appropriate)	X		X 		X 	$X^5$	X 			X 
Document any educational activities			$X^6$		$X^6$	$X^6$	$X^6$			$X^6$
Study Material Management										
Dispense Tempo Smart Button	X								X 	
Dispense Humalog Tempo Pens	X		X						X 	

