## 9.3.2. Secondary Endpoints

The following endpoints will be calculated and analysed with the model described in Section 9.3 for the masked and unmasked periods:

- Change in participant CGM TIR ( $\geq$ 70 and  $\leq$ 180 mg/dL).
- Change in participant CGM TAR (>180 mg/dL and >250 mg/dL).
- Change in participant CGM TBR (<54 mg/dL and  $54 \text{ mg/dL} \le X < 70 \text{ mg/dL}$ ).
- Change in mistimed bolus dose [0,1] administering a bolus dose from the start of a glucose excursion to 1 hour after the start of glucose excursion and before the peak of the glucose excursion, is classified as a mistimed bolus dose. The definition of a glucose excursion remains the same for an MBD.
- Change in correction boluses taking a bolus dose after the peak of a glucose excursion but within 4 hours from the start of a glucose excursion and prior to start of next glucose excursion.
- Change in insulin doses: basal and mealtime, ratio basal/mealtime, dose per meal as well and total dose in IU/kg.
- Correlations between MBD/mistimed bolus and:
  - o TIR
  - o TAR
  - o TBR, and
  - o HbA1c.
- Other secondary analyses:
  - o evaluate coefficient of variation (from CGM data)
  - o evaluate mean sensor glucose (from CGM data).
- Exploratory analyses:
  - o change in HbA1c from baseline (Visit 1) to Visit 7 (last visit),
  - o healthcare professional questionnaires, and
  - o participant questionnaires
  - o day and night time CGM profiles during the two periods.

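### The HbA1c MMRM in SAP 4.5.1 requests a study-period difference that does not exist, because each participant has only one HbA1c change value

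*SAP*

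**What the plan says.** Protocol 9.3.2 lists as an exploratory analysis the "change in HbA1c from baseline (Visit 1) to Visit 7 (last visit"). SAP 4.5.1 gives the summary: "Actual HbA1c values at baseline (Visit 1) and Visit 7 and change from baseline will be presented in a table using descriptive continuous statistics". It then adds a model: "In addition, an MMRM will be run on this data". The example code contains:

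- outcome and fixed effects: "Model HbAlc_change = StudyPeriod BaseBMI BaseHbAlc week/ ddfm = kenwordroger" (spelling as in the SAP), with StudyPeriod and week as class variables;
- a random intercept: "Random usubjid / subject = usubjid";
- an unstructured residual covariance over week: "Repeated week/ subject = usubjid type = un rcorr";
- the requested result: "Lsmeans StudyPeriod/diff cl pdiff".

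In the Schedule of Activities (Protocol 1.3), the row "HbA1c PoC Test" is marked at Visit 1, Visit 7 and early termination. It is not marked at Visit 3, which ends Study Period 1.

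**The concern.** The template comes from SAP 4.3.2. There each participant has six weekly rows, two in Study Period 1 and four in Study Period 2, so period and week both vary within a person. HbA1c has no such rows. The only change is from Visit 1 to Visit 7. It belongs to Study Period 2, and there is no Study Period 1 change to set against it.

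At stake is the one model-based result planned for HbA1c. The SAP asks for a period difference with an interval and p-value. The data cannot supply that difference, and the SAP names no other HbA1c model.

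**Working it through.** The plan states no figure for this analysis, so there is none to reproduce. The check counts records and parameters. The sample sizes are 24 (the minimum with analysable data, Protocol 9.4), 32 (50 × (1 − 0.35) = 32.5, rounded down) and 50 (planned enrolment). Baseline BMI and HbA1c values were simulated, because only the rank of the design matters.

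**1. As specified: one Visit 7 change row per participant**
- Fixed-effect columns: intercept 1 + StudyPeriod 1 + BMI 1 + HbA1c 1 + week 1 = 5.
- The StudyPeriod and week columns are all ones and repeat the intercept. The rank is 5 − 2 = 3 at n = 24, 32 and 50.
- StudyPeriod has one level, so there is no pair of least-squares means to subtract.
- Covariance: the variance of each record is σ²(participant) + σ²(residual), and records are independent. That is two parameters with one identifiable quantity, their sum.
- With one record per participant at a common week, the unstructured form and each of the six fallback structures in SAP 4.3.2 reduce to a single variance. None of them helps.

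**2. With an added baseline row, change = 0**
- Columns: 1 + 2 + 1 + 1 + 2 = 7. The rank is 4, and still 4 without week. Period and week are the same variable, and the separate StudyPeriod contrast is not estimable.
- The baseline outcome is zero for everyone and has no variance. The unstructured 2 × 2 matrix (3 parameters) plus a random intercept (1) gives 4 parameters for 3 moments.

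**3. With some early-termination rows**
- Assumed for illustration (n = 32): three participants stop at three different weeks, two of them in Study Period 1.
- Columns: 1 + 2 + 1 + 1 + 4 = 9. The rank is 6, and still 6 without StudyPeriod. The contrast is not estimable. Each person still has one change, so any comparison would be between different people.

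**4. What layout 1 does contain**
- The least-squares mean has coefficients (1, 1, mean BMI, mean HbA1c, 1). This vector is the average of the design rows, so it lies in the row space and is estimable.
- Its standard error depends only on the sum of the two variances. On simulated data at n = 24, 32 and 50, the least-squares mean and its standard error equalled the intercept and standard error from a regression on mean-centred BMI and HbA1c.

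**5. Precision of a mean change**
- The documents give no SD for HbA1c change, so the result is in units of that SD. For a paired mean the 95% half-width is t(0.975, n − 1)/√n.
- n = 24: 2.069/4.899 = 0.42 SD. n = 32: 2.040/5.657 = 0.36 SD.
- The regression has n − 3 degrees of freedom. The half-widths are 2.080/4.899 = 0.42 and 2.045/5.657 = 0.36 of the residual SD.

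**The case against.** A reader might infer that the model cannot be fitted, or that it yields no test or interval for HbA1c change. The documents do not support either. The outcome in the code is already the change, and step 4 shows that its single least-squares mean is estimable and does not depend on how the variance is split. Software may drop the aliased terms and print that mean with an interval. What it cannot give is the period difference. The redundant variance terms may also bring convergence warnings or unreliable degrees of freedom.

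A reader might also infer that a replacement must be chosen after the data are seen. That does not follow. The defect is visible from the visit schedule and can be corrected before lock. The planned table gives the mean and SD of change, from which, with the number of participants, a paired t-test and interval follow by arithmetic. The code is labelled as an example, and SAP 4.1 provides for changes of method to be justified in the clinical study report.

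Finally, HbA1c is exploratory, and SAP 1.1 defines its endpoint as summary statistics, which the table delivers. These arguments limit the consequence. They do not remove the error: the text commits to an MMRM, the flexibility in SAP 4.3.2 singles out the covariance structure, and no substitute is named.

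Modelling actual HbA1c with two rows per participant would let period vary. It is a different model, however: period would coincide with visit, and the baseline covariate would equal the outcome at Visit 1.

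**Conclusion.** The model in SAP 4.5.1 is mis-specified for HbA1c. With one change value per participant, StudyPeriod and week are aliased with the intercept, the requested difference between periods does not exist, and only the sum of the two variances is identifiable. The mean change itself can still be estimated.

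The severity is minor. The model is an addition to an exploratory endpoint, its descriptive table is intact, and the defect has no bearing on the sample size or on the results for the primary and secondary endpoints. The conclusion rests on the visit schedule and the printed code and on no numerical assumption. Early-termination values do not change it.

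The estimable quantity runs from Visit 1 to Visit 7 and so spans the run-in as well as the intervention period. It should not be labelled a difference between study periods.

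**What to change.** Before database lock, amend SAP 4.5.1 as follows.

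1. Remove StudyPeriod, week, the RANDOM and REPEATED statements and the LSMeans difference.
2. Pre-specify one analysis: a linear regression of HbA1c change (Visit 7 minus Visit 1) on baseline HbA1c and baseline BMI, each centred at its mean among the participants analysed. Report the intercept as the adjusted mean change, with its 95% CI and p-value.
3. State how early-termination HbA1c is handled. The endpoint is defined at Visit 7, so use Visit 7 values for the main result and add early-termination values only as a sensitivity check.
4. Keep the descriptive table as planned.

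The cost is a few lines of SAP text and shorter code. No new data, visits or participants are needed.

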4.5.2. Outcome of Study IORW Healthcare Professional Questionnaires

Responses from HCP questionnaires from initiation and end of study will be summarized.

4.5.3. Outcome of Study IORW Participant Questionnaires

Responses from participant questionnaires from Visits 1 (baseline), Visit 3 (end of Study Period 1), and Visit 7 (end of study) will be summarized using shift tables.

4.5.4. Continuous Glucose Monitoring Curves Integrated with Data Received from the Tempo Pen/Smart Button

The MBD and mistimed bolus dose will be calculated using CGM plots and algorithm explained in Section 4.3.1.1. The association between MBD and mistimed bolus doses with TIR, TAR, TBR and HbA1c will be analyzed using the Spearman rank order correlation. This analysis will be done on the sensitivity analysis set.

4.5.5. Glooko Research Mobile Application Use Data

Glooko mobile application data including the number of connections to the application, number of uploads from CGM, number of data uploads, percentage of CGM data available, number of insulin data available, and number of prime before injection will be summarized in a table by study period.

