#### **Exploratory:**

- 1) Summary statistics of actual and change in HbA1c between baseline and Visit 7
- 2) Outcome of IORW HCP questionnaires
- 3) Outcome of IORW participant questionnaires
- 4) CGM curves integrated with data received from the Tempo Pen/Smart Button
- 5) Glooko Mobile App data (e.g., number of connections to the app, number of uploads from CGM, number of CCL data uploads, % of CGM data available, number of insulin data available) and comparison of Study Period 1 and Study Period 2 app use
- 6) Summary of CGM wear time data and correlation with MBD data and differences between Study Period 1 versus Study Period 2
- 7) HFS-SF questionnaire score between Visit 1 and Visit 7 and MBD data.
- 8) Summarize nighttime (00:00 AM to 06:00 AM) and daytime CGM profiles during the masked/ unmasked periods.

Abbreviations: B = breakfast; CGM = continuous glucose monitoring; D = dinner; HbA1c = glycated haemoglobin; HCP = healthcare professional; IORW = Study F3Z-MC-IORW; L = lunch; MBD = missed bolus dose; MDSW = medical device software; TAR = time above range; TBR = time below range; TIR = time-in-range.

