## 4. Study Design

## 4.1. Overall Design

Study IORW is a multicentre, open-label, controlled, single-arm, pragmatic outpatient study in participants with T1D or T2D that comprises 2 study periods, including:

- a 6-week run-in period (Study Period 1) when insulin timing and dosage data

  CCI is masked to the participant using Glooko RMA and is unmasked to the HCP using Glooko HCP platform, and
- a 12-week intervention period (Study Period 2) when insulin timing and dosage data

  CCl is unmasked to the participant using Glooko RMA and the HCP using Glooko HCP platform.

Study IORW will be carried out in France and will include 9 clinical study sites. The study is expected to last approximately 16 months, with each participant duration of approximately 18 weeks. Approximately 50 participants will be enrolled in the study. Best efforts will be made to enrol a participant ratio of 4:1 for participants with T1D to participants with T2D.

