Site personnel will review hypoglycaemia management and provide appropriate training to participants (see Section 2.4.3.1).

For a complete list of all required activities, please refer to the SoA (Table 1.1).

#### 4.2.3. Visit 2 - Remote Check-in 1

Visit 2 will be conducted approximately 1 week after Visit 1. Site will perform a remote check-in in which they will review the understanding and use of the study components with participants.

During the visit, the site staff will:

- collect DDs
- collect AEs
- review concomitant medications/changes in medications
- review the functioning, understanding, and use of the study platform components, and
- confirm up-to-date participant CGM and Tempo Pen/Smart Button data was uploaded to the RMA

For a complete list of all required activities, please refer to the SoA (Table 1.1).

## 4.2.4. Visit 3 - In-Person Check-in 1

Visit 3 will be conducted approximately 5 weeks after Visit 2.

At Visit 3, the participant will be required to visit the study site with his/her:

- mobile device with RMA
- CGM
- Dexcom receiver
- Tempo Pen(s) currently in use, and
- Tempo Smart Button.

Unused Tempo Pen(s) may remain at the participant's residence so long as he/she checks how much is remaining to aid in resupply calculations.

During the visit, the site staff will:

- collect DDs
- collect AEs
- review concomitant medications/changes in medications
- review study supplies and dispense, as needed
- review the functioning, understanding, and use of the study platform components
- confirm up-to-date participant CGM data was uploaded to the RMA
- administer IORW Participant V3 Questionnaire
- administer HFS-SF Questionnaire, and
- weigh the participant.

For a complete list of all required activities, please refer to the SoA (Table 1.1).

In addition, following completion of the IORW Participant Visit 3 Questionnaire and HFS-SF Questionnaire, the site staff will unmask the CC data, review the participants' dosing patterns, and discuss information from the HCP Portal with the participant about his/her dosing habits and glucose control collected during Study Period 1.

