#### To accomplish this:

- HCPs will be able to display Study Period 1 data on the HCP Portal which will contain previously participant-masked information about insulin dosing and glycaemic status
- the investigator or designee will review Study Period 1 data
- the investigator or designee will share and discuss the data collected during Study Period 1 with the study participant
- dose adjustments and other advices provided by the HCP will be recorded, and
- any educational activities that would result from the review of the report would be documented by the HCP.

#### 4.2.5. Visit 4 - Remote Check-in 2

Visit 4 will occur approximately 1 week after Visit 3. At Visit 4, site staff will perform a remote check-in during which they will review the understanding and use of the study components with participants.

During the visit, the site staff will:

- collect DDs
- collect AEs
- confirm up-to-date participant CGM and Tempo Pen/Smart Button data was uploaded to the RMA
- review concomitant medications/changes in medications, and
- review the functioning, understanding, and use of the study platform components.

For a complete list of all required activities, please refer to the SoA (Table 1.1).

#### 4.2.6. Visit 5 and 6 – Remote Check-in 3 & 4

Visit 5 will occur approximately 3 weeks after Visit 4.

Visit 6 will occur approximately 4 weeks after Visit 5.

Site staff will perform a remote check-in with the participant during which they will:

- collect DDs
- collect AEs
- review concomitant medications/changes in medications
- review the functioning, understanding, and use of the study platform components (if deemed necessary based on previous visits)
- confirm up-to-date participant CGM and Tempo Pen/Smart Button data was uploaded to the RMA
- share and discuss glucose control and insulin dosing habits (adjust the dose if appropriate) with the participant (from last data review, i.e., approximately 4 weeks)
- document any educational activities that would result from the review of the report by the HCP, and
- review study supplies status.

For a complete list of all required activities, please refer to the SoA (Table 1.1).

#### 4.2.7. Visit 7 – In-Person Check-in 2

Visit 7 will occur approximately 4 weeks after Visit 6.

At Visit 7, the participant will be required to visit the study site and bring his/her:

- mobile device with RMA
- CGM
- Dexcom receiver
- Tempo Pen(s) currently in use
- unused Humalog Tempo Pen(s), and
- Tempo Smart Button.

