### 4.4. Scientific Rationale for Study Design

### 4.4.1. Rationale for Investigation of Missed Bolus Dose

This study objectively estimates:

- MBDs and their relationship to short-term glycaemic control are clinically relevant, and
- participant behaviour and satisfaction among participants.

There is no standard-of-care or comparator arm because the primary objective of this study is to objectively estimate MBDs from reliable automated collection, which can only happen if the participant uses a smart insulin pen recording the injections. Therefore, the last 2 weeks of Study Period 1 (Week 5 to Week 6 [Visit 3]) will be used for analyses with masked RMA as baseline data.

The study duration of 18 weeks (6 weeks +12 weeks) is long enough for the assessment of MBDs in a study setting. Each enrolled participant must be on a mealtime bolus insulin regimen with at least 3 or more bolus doses daily (Section 5.1).

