1.2. Study Design

1.2.1. Overall Design

Study F3Z-MC-IORW (IORW) is a multicenter, open-label, controlled, single-arm pragmatic outpatient study in participants with T1D or T2D that comprises of 2 study periods, including:

- a 6-week run-in period (Study Period 1) when insulin timing and dosage data

 CCl is masked to the participant using the Glooko® Research Mobile Application (RMA) and is unmasked to the healthcare professional (HCP) using the Glooko HCP platform, and
- a 12-week intervention period (Study Period 2) when insulin timing and dosage data

[figure not shown]
 CCI is unmasked to the participant using the Glooko RMA and the HCP using the Glooko HCP platform.

Study IORW will be carried out in France and will include up to 10 clinical study sites. The study is expected to last approximately 16 months, with each participant duration of approximately 18 weeks. Approximately 50 participants will be enrolled in the study. Best efforts will be made to enroll a participant ratio of 4:1 for participants with T1D to participants with T2D.

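### SAP 4.5.5 tabulates app-use counts over a 6-week and a 12-week period with no denominator, so steady weekly use would read as roughly a doubling after unmasking

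*SAP*

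**What the plan says.** SAP Section 4.5.5 names six app-use items. Five are counts: connections to the app, uploads from the CGM, data uploads, insulin data available, and primes. One is a percentage, the share of CGM data available. The section closes with "number of prime before injection will be summarized in a table by study period". It states no rate, no common window, no analysis set and no allowance for time observed.

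The purpose goes beyond description. Exploratory endpoint 5 in Protocol Table 3.1 includes a "comparison of Study Period 1 and Study Period 2 app use", and SAP Section 1.1 carries the same comparison. The paired objective is to relate app interaction to the change in MBDs between the periods.

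The periods differ in length. SAP Section 1.2.1 describes "a 6-week run-in period (Study Period 1) when insulin timing and dosage data" are masked to the participant, followed by "a 12-week intervention period (Study Period 2) when insulin timing and dosage data" are unmasked.

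Elsewhere the SAP does scale for time. Section 4.3.1.1 divides the MBD total by the number of days with evaluable CGM data and multiplies by 7. That formula is given for MBDs only.

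**The concern.** A raw count is a weekly rate multiplied by the weeks observed. When one period is twice as long as the other, a table of counts mixes engagement with exposure time. A reader comparing the two columns could take the extra six weeks for a response to unmasking.

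The artefact also points the way one would expect a real effect to point. In Study Period 1 the insulin data are hidden from the participant and the reminder feature is not to be used (Protocol Sections 4.1.1 and 4.2.2.2), so higher use after unmasking is plausible. An increase caused by period length would be easy to accept as real.

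The same mixing reaches the stated objective of relating app use to change in MBDs. The MBD side is a weekly rate. The app-use side, as written, is not.

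**Working it through.** **1. Reproduce the period lengths.** Protocol Section 4.4.1 says "The study duration of 18 weeks (6 weeks +12 weeks) is long enough for the assessment of MBDs in a study setting". The visit intervals in Protocol Table 1.1 agree.
- Period 1: Visit 1 to 2 is 1 week, and "Visit 3 will be conducted approximately 5 weeks after Visit 2" (Protocol 4.2.4). 1 + 5 = 6 weeks.
- Period 2: the intervals from Visit 3 to Visit 7 are 1, 3, 4 and 4 weeks, the last being "Visit 7 will occur approximately 4 weeks after Visit 6" (Protocol 4.2.7). 1 + 3 + 4 + 4 = 12 weeks.
- Total: 6 + 12 = 18 weeks, which matches.

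**2. Ratio at unchanged weekly use.** Expected count = weekly rate × weeks observed. With the same rate r in both periods, the ratio is 12r / 6r = 2.0. With an assumed 7 connections a week, the counts are 42 and 84; per week they are 7 and 7, a ratio of 1.0.

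**3. What a real change would look like.** Count ratio = true rate ratio × 2.
- Weekly use halves: 0.5 × 2 = 1.0, which reads as no change.
- Weekly use falls by 25%: 0.75 × 2 = 1.5, which reads as a rise.

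**4. Other windows in the SAP.** SAP Section 6.2 ties Weeks 5–6 and Weeks 15–18 to the primary and secondary objectives; app use is exploratory. If those windows were used anyway, the ratio is 4/2 = 2.0.

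**5. Visit windows.** Visits 3 and 7 may each be up to 7 days late.
- Only Visit 3 late, with Period 2 kept at 84 days: 84/49 = 1.71.
- Only Visit 7 late: 91/42 = 2.17.
- Extreme case, with every visit window used to its limit and the shifts adding up: (84 − 9)/(42 + 10) = 1.44 to (84 + 9 + 7)/(42 − 3) = 2.56.

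**6. Dropout.** The documents assume 35%, a figure that also covers missing CGM data, and give no timing. Assume departures spread evenly over 18 weeks, so the share remaining at week t is S(t) = 1 − d × t/18. At d = 0.35:
- Period 1 weeks per enrolled participant: 6 × S(3) = 6 × 0.9417 = 5.65.
- Period 2 weeks per enrolled participant: 12 × S(12) = 12 × 0.7667 = 9.20.
- Ratio of pooled totals: 9.20/5.65 = 1.63.
- Ratio of means per participant entering each period: S(6) = 0.8833, 9.20/0.8833 = 10.42 weeks, and 10.42/5.65 = 1.84.

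At d = 0 both ratios are 2.00. Steps 5 and 6, leaving out the extreme case, give the range of roughly 1.6 to 2.2.

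**7. Early leavers at the same engagement.** Leaving after 6 unmasked weeks: 6/6 = 1.0. The main analysis set admits early discontinuers with at least 20 days of CGM data in Period 2 (SAP Section 3). Someone observed for 20 unmasked days shows 20/42 = 0.48, against 2.0 for a completer. Section 4.5.5 does not say whether that set applies.

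**8. Effect on a correlation.** Take illustrative rates. A participant steady at 10 connections a week has a raw difference of 120 − 60 = +60. One who doubles from 2 to 4 a week has 48 − 12 = +36. The participant with no change ranks higher. On weekly rates the changes are 0 and +2, and the order is right.

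**The case against.** The strongest reply is that Section 4.5.5 is silent on a denominator and does not commit to raw totals. Scaling of this kind is often settled in table shells, which are not part of these documents. A reader might infer that the sponsor plans to report a doubling. The text does not say so. What stands is that nothing pre-specifies a rate, and the section followed as written yields counts. Two related summaries do not supply one: app exposure by period and overall (Protocol 9.3.4) and usable CGM and pen data (SAP 6.3).

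A second reply is that not every count accrues evenly over time. Set-up and training fall in Period 1 and may add connections there. CGM uploads may follow the visits. With one upload per visit, Visits 2–3 against 4–7 give 4/2 = 2.0, and adding the Visit 1 transfer check in Protocol Table 1.1 gives 4/3 = 1.33. This stands, so the inference that every participant will look exactly twice as engaged is not supported.

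A third reply concerns the correlation. A reader might infer that the planned correlation with MBD change is invalid. Section 4.5.5 specifies no correlation, unlike 4.5.6 and 4.5.7. A Spearman coefficient on Period 2 counts, or on the ratio of periods, would keep its ranks among participants observed for the same lengths of time. Distortion arises with unequal follow-up or with a raw difference, and no document says which variable will be used. That gap is itself a reason to define it.

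**Conclusion.** The point holds for the five unscaled counts in Section 4.5.5. For those that accrue steadily, unchanged weekly use would appear as a Period 2 to Period 1 ratio of about 2. The range is roughly 1.6 to 2.2 when either the late-visit windows at Visits 3 and 7 or evenly spread dropout of up to 35% is allowed for. Early leavers would show lower ratios at the same engagement. Exact doubling needs full nominal periods and a constant weekly rate. The dropout timing and the example rates are assumptions.

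The severity is low. The endpoint is exploratory and the section plans no test. It would be wrong to infer any effect on the primary result: MBDs are already scaled per week, and no secondary endpoint depends on app-use counts. What is at stake is how app engagement after unmasking is read, and any link drawn from it to change in MBDs.

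**What to change.** In SAP Section 4.5.5:

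- Report each count as a rate per participant-week: count divided by days observed in that period, multiplied by 7. End the observed days at the period boundary or at discontinuation, whichever comes first.
- State the weeks used (whole periods, or Weeks 5–6 and 15–18) and the analysis set.
- Leave the percentage of CGM data available as it is.
- For the SAP 1.1 objective, name the correlation method and use the weekly rate or its change as the app-use variable.

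Raw totals can stay in the table beside the rate. The cost is one division per count from dates already held, with no new data and no change to study conduct. Under SAP Section 4.1 only a change to a principal feature of the protocol requires an amendment, and an added denominator for an exploratory summary should not reach that threshold.
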